10.2.2. Secondary efficacy endpoints analyses

All secondary endpoints (duration of treatment benefit over 12 weeks and mean change from baseline over 12 weeks in FAACT-F 12-items, FACIT-F and FAACT total score in the secondary efficacy endpoints) will be analyzed using the same statistical model and multiple imputation approach as for the co-primary efficacy endpoints. Details are reported in Section 10.1.2 and Appendix12.1.

10.2.3. Secondary efficacy analysis on subgroups

For all secondary efficacy endpoints, analyses will be conducted on the ITT Set based on the subgroups defined in Section 8.6. The statistical analyses and models will be based on the models used for the secondary endpoints described in Section 10.2.2. For subgroups defined based on a stratification factors, the corresponding variable will be excluded from the model for the analysis.

Forest plots will be done presenting point estimates and 95% confidence intervals of each secondary efficacy endpoints.

10.3. Exploratory Endpoints

Business & Decision

Life Sciences

All the analyses of the exploratory endpoints will be conducted on the ITT. See Section 6.1.3 for the list of exploratory endpoints which will be analyzed.

The datasets imputed for the primary and secondary efficacy endpoints will be used also for the analysis of the exploratory endpoints.

10.3.1. Exploratory endpoints derivation.

All the rules defined for the derivation of the primary and secondary endpoints apply to the exploratory endpoints as relevant.

10.3.1.1. *Mean Change from baseline over X Weeks*

Mean Change in Body Weight, in 5-IASS and in FAACT total score from baseline over 6, 9, 15, 18, 21, and 24 Weeks are derived as the primary efficacy endpoint (see Section 10.1.1).

For instance:

Mean change in Body Weight from baseline over 24 Weeks is calculated as the sum of the changes from baseline over 24 weeks by the time of the last assessment (either week 24 or before in case of death), and then divided by the number of assessments (observed or imputed) from baseline up to the time of the last assessment (either week 24 or before, in case of death).

10.3.1.2. *Percentage of Change in Body Weight*

Percentage of change in body weight from baseline computed as (Weight at Visit – Baseline) / Baseline * 100

T AN001 Effective Date 25 JUL 2022 Approved Version 2.00

10.3.1.3. Composite Clinical Response (CCR)

CCR is a composite measure defined as:

- 1.5 kg body weight gain from baseline and
- ≥ 3 points gain in the 5-item Anorexia Symptom Subscale score from baseline.

The two components of CCR are derived as follows:

- Achievement of 1.5 kg gain in body weight from baseline computed as
 - If change in body weight ≥ 1.5 kg then "Responder"; otherwise "Non-responder"
- Achievement of ≥ 3 points increase in 5 I-ASS from baseline computed as
 - If (5-IASS at Visit Baseline) ≥ 3 then "Responder"; otherwise "Non-responder"

CCR is then computed as

 If "Responder" in Achievement of ≥ 1.5 kg gain in body weight, and If "Responder" in Achievement of ≥ 3 points increase in 5-IASS, and If patient is alive then "Responder"; otherwise "Non-responder"

10.3.1.4. Achievement of responder threshold

At each visit:

- "Responder" if value >= clinically meaningful threshold and patient is alive
- "Non-responder" otherwise

Definition of Clinically meaningful threshold is given in Section 8.8.

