6.1.3. Exploratory Efficacy Endpoints

- Mean change in body weight from baseline over 6, 9, 15, 18, 21, and 24 weeks.
- Mean change in patient-reported anorexia symptoms from baseline over 6, 9, 15, 18, 21, and 24 weeks, as measured by the 5-item Anorexia Symptom Subscale.
- Mean change in FAACT total score from baseline over 6, 9, 15, 18, 21, and 24 weeks.
- Composite Clinical Response (CCR) at Week 3, 6, 9, 12, 15, 18, 21, and 24.
- Change in body weight from baseline to Week 3, 6, 9, 12, 15, 18, 21, and 24.
- Change in patient-reported anorexia symptoms from baseline to Week 3, 6, 9, 12, 15, 18, 21, and 24, as measured by the 5-item Anorexia Symptom Subscale.
- Clinically meaningful gain in body weight (1.5 kg) from baseline to Week 3, 6, 9, 12, 15, 18, 21, and 24.
- Clinically meaningful increase in 5-item Anorexia Symptom Subscale (3 points) from baseline to Week 3, 6, 9, 12, 15, 18, 21, and 24.

- Percentage of change in body weight from baseline to Week 3, 6, 9, 12, 15, 18, 21, and 24.
- Changes from baseline to Week 3, 6, 9, 12, 15, 18, 21, and 24 in the FAACT total score, FACT-G total score, FAACT TOI, the 12-item A/CS domain and the 4-item Anorexia Concerns Subscale.
- Changes from baseline to Week 3, 6, 9, 12, 15, 18, 21, and 24 in the Functional Assessment of Chronic Illness Therapy-Fatigue (FACIT-F) domain as well as the FACIT-F TOI score.
- Changes from baseline to Week 3, 6, 9, 12, 15, 18, 21, and 24 in the Hunger Assessment Scale.
- Changes from baseline to Week 6 and 9 in the Patients' Global Impression of Severity (PGIS) scale and the Patients' Global Impression of Change (PGIC) scale at Week 6 and 9.
- Changes from baseline to Week 3, 6, 9, 12, 15, 18, 21, and 24 in the following items extracted from Physical Well-Being and Functional Well-Being domains:
 - GP1, GP7, GF5, GF6, GF7.

Life Sciences

- Changes from baseline to Week 3, 6, 9, 12, 15, 18, 21, and 24 in the following items extracted from the 12-item A/CS domain:
 - ACT1, ACT2, ACT4, ACT13.
- Changes from baseline to Week 3, 6, 9, 12, 15, 18, 21, and 24 in the following items extracted from the FACIT-F (Fatigue) questionnaire:
 - HI7, HI12, AN2, AN5, AN12.
- Correlation between Weight gain and improvement on the patient reported anorexia score from baseline to Week 3, 6, 9, 12, 15, 18, 21, and 24.
- Correlation between Weight gain and improvement on the patient reported anorexia score from baseline over 12 weeks.

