A patient will be defined as having "completed" 24 weeks treatment when the patient received study drug at the day of Visit 10 (either on-site or at home) and have evidence of treatment for all previous weeks.

Fluid retention

Presence of fluid retention will be assumed when either a treatment emergent AE associated with fluid retention is present or edema is recorded in the CRF by investigator at time of the assessment of weight. Specific assessments are scheduled at each study visit.

After a specific review of the LLTs during the BDRM, AEs coded with the following PTs were confirmed as possibly impacting the weight measurements: 'Fluid retention', 'Ascites', 'Pleural effusion', 'Oedema peripheral', 'Oedema'. These AEs will be taken into account.

Clinically meaningful thresholds for 5-IASS change and Body Weight Change

To support with patient informed interpretation of meaningful change or stabilization, the results of a quantitative analysis of a separate study (7), combined with evidence from the embedded qualitative interview sub-study (6), support a responder definition of 3.0 for the 5-IASS Score and 1.5 kg weight gain for body weight.

These thresholds were defined in line with FDA guidance, therefore anchor-based methods for score interpretation were considered the primary analysis. Distribution-based methods were used as supportive and secondary analysis using PGIS (Patient Global Impression of Severity) and PGIC (Patient Global Impression of Change) as anchors.

For the analysis of the duration of treatment benefit the definition of a threshold to establish a change from baseline as clinically meaningful is provided (Sections 10.2 and 10.2.1)

Last value

Business & Decision

Life Sciences

For Laboratory Shift Tables analysis, the Last Value is the last value reported by the patient during the study period.

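### SAP 10.3.1.4 tests the visit value, not the change from baseline, against the responder threshold, at odds with the rest of the SAP

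*SAP*

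**What the plan says.** SAP 10.3.1.4 gives the derivation for the two endpoints on achieving the responder threshold. At each visit the patient is a responder "if value >= clinically meaningful threshold and patient is alive" and a non-responder otherwise. It then points elsewhere for the threshold: "Definition of Clinically meaningful threshold is given in Section 8.8".

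The related sections read as follows:

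- **SAP 8.8** heads the definition "Clinically meaningful thresholds for 5-IASS change and Body Weight Change" and says that the evidence cited there serves to "support a responder definition of 3.0 for the 5-IASS Score and 1.5 kg weight gain for body weight".
- **SAP 6.1.3** lists the endpoints as "Clinically meaningful gain in body weight (1.5 kg) from baseline to Week 3, 6, 9, 12, 15, 18, 21, and 24" and "Clinically meaningful increase in 5-item Anorexia Symptom Subscale (3 points) from baseline to Week 3, 6, 9, 12, 15, 18, 21, and 24". Protocol 3.1.3 also frames them as a gain or increase from baseline.
- **SAP 10.3.1.3**, directly above, derives the same two flags as components of the CCR. For weight it says "If change in body weight ≥ 1.5 kg then" responder; for 5-IASS it subtracts baseline and compares the difference with 3.
- **SAP 10.2.1** defines duration of benefit by comparing change from baseline with the threshold.
- **SAP 10.3.2.3** analyses the flags by logistic regression.

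**The concern.** Section 10.3.1.4 is the operative rule for these two endpoints, and it names the wrong quantity. The SAP mostly uses *value* for the measurement itself: 8.3.1 calls weight a raw value, and 8.8 defines baseline as the value collected at Visit 2. Change has its own definition and formula in 8.8 and again in 10.3.1.5. A programmer who follows 10.3.1.4 as written would compare a body weight in kilograms with 1.5 kg, and a 0–20 score with 3.

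The weight-responder table would then describe survival rather than weight response. The 5-IASS table would describe who scores at least 3 rather than who improved. Neither could be reconciled with the CCR table, whose components use change. SAP 12.4 has outputs checked for consistency with the SAP. As the text stands, a program faithful to 10.3.1.4 fails against 6.1.3, and a program faithful to 6.1.3 departs from 10.3.1.4.

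**Working it through.** The plan gives no figure to reproduce here. The check applies the rule both ways.

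**Inputs**

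- Thresholds: 1.5 kg and 3 points (SAP 8.8).
- Lower limit for an imputed weight: 30 kg (SAP 12.1.1.2).
- 5-IASS range: 0–20 (SAP 12.3).
- Entry limit for 5-IASS: at most 17 (Protocol 4.3.2, criterion 5).
- Patients who have died count as non-responders (SAP 10.3.1.4 and 12.1.1.2).

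**Rules compared**

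- Literal: responder if visit value ≥ threshold and alive.
- Change: responder if visit value − baseline ≥ threshold and alive.

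**Weight.** 30 / 1.5 = 20, so every imputed weight exceeds the threshold at least twentyfold. No observed adult weight falls below 1.5 kg. Every living patient with a weight is therefore a literal responder. Illustrative weights (assumed):

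| Baseline → visit (kg) | Change | Literal | Change rule |
|---|---|---|---|
| 50 → 51.5 | +1.5 | responder | responder |
| 50 → 51.4 | +1.4 | responder | non-responder |
| 50 → 50 | 0 | responder | non-responder |
| 50 → 45 | −5 | responder | non-responder |

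**5-IASS.** Take integer baselines b = 0 to 17 and visit scores v = 0 to 20.

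- All pairs: 18 × 21 = 378.
- Literal responders (v ≥ 3): 18 baselines × 18 scores = 324.
- Change-rule responders (v ≥ b + 3): there are 18 − b scores for each b, so 18 + 17 + … + 1 = 171.
- Every change-rule responder has v ≥ 3, so the rules disagree in 324 − 171 = 153 pairs.
- Of these, worsened but counted as responder (3 ≤ v < b): b − 3 scores for each b from 4 to 17, so 1 + 2 + … + 14 = 105.
- The other 153 − 105 = 48 pairs are unchanged or improved by only 1 or 2 points.

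For example, 10 → 4 and 15 → 3 are literal responders although both patients worsened; 10 → 13 is a responder under both rules.

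**Effect on the logistic model.** Under the literal rule the weight outcome is 1 if alive and 0 if dead. Its odds ratio at a visit would compare being alive between arms, under a label of weight response.

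**The case against.** The strongest reply is that the line does not stand alone. Its next sentence sends the reader to 8.8, where the thresholds are headed as change thresholds and the weight figure is a gain, and a gain can only sensibly be compared with a change. SAP 12.1.1.2 also uses *value* for derived quantities, including change from baseline, so the word need not mean the raw measurement. SAP 10.3.1 carries the primary and secondary derivation rules over to exploratory endpoints where relevant, and nowhere is response defined by absolute weight.

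Most of this stands. A reader might infer from 10.3.1.4 that the SAP has chosen to classify by visit value. The documents do not support that: read together, they intend change from baseline. What remains is that the operative sentence does not say so, while the subsection above it does. The carry-over rule helps only in part, because the worked example in 10.2.1 also labels its inputs as assessment values while setting the line equal to the threshold.

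A reader might also infer that under the literal rule the logistic model could not be fitted, since everyone would respond. That does not hold in general. Deaths count as non-responders and the analysis is on the ITT set, so once deaths have occurred the outcome varies. It would be constant only at a visit with no earlier deaths.

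**Conclusion.** This is a wording defect in a stated derivation rule, and it is minor. Followed literally, 10.3.1.4 turns the weight flag into an indicator of being alive and makes the 5-IASS flag disagree with the change rule in 153 of 378 possible pairs, 105 of them worsenings. The pair count assumes integer scores and a baseline of at most 17. That limit is checked at screening, whereas baseline is normally the Visit 2 score and could be higher. The pairs are not weighted by how often they occur, so the count says nothing about the proportion of patients who would be misclassified.

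The reach is two exploratory endpoints at eight visits, which SAP 10.3.2 places outside the control of Type I error. The co-primary and secondary tests are unaffected. The documents do not show how the flags were programmed; the mock tables are in a separate document (SAP 12.5).

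**What to change.** Replace the rule in SAP 10.3.1.4 with: Responder if the change from baseline at the visit is ≥ 1.5 kg (weight) or ≥ 3 points (5-IASS) and the patient is alive at that visit; otherwise Non-responder. Confirm that the program derives both flags this way and that they agree with the CCR components in 10.3.1.3.

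The cost is one line of text and one program check, with no change to any endpoint, threshold or model. If the final SAP is not reissued, a dated clarification in the study report would do, since Protocol 9 allows changes to be documented there.

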10.3.1.5. Change from baseline

Changes from baseline to Weeks 3, 6, 9, 12, 15, 18, 21, and 24 are derived as:

("variable" at Visit – Baseline).

10.3.2. Exploratory endpoints analyses.

The exploratory efficacy analyses are aimed to explore the effect of the anamorelin on different endpoints but are not part of the Type I error multiplicity adjustment, thus have no confirmatory value.

10.3.2.1. Mean Change from baseline over X Weeks

The exploratory endpoints based on the "mean change from baseline over X Weeks" will be computed and analyzed like the main analysis for the primary efficacy endpoints.

10.3.2.2. Change from baseline

All the exploratory endpoints based on the "change from baseline" except the HAS and the PGIS/C will be analyzed using an ANCOVA model, with explanatory variables being the randomized treatment, the stratification factors and the baseline value.

The estimator of the effect will be the difference in change from baseline between the test group and the placebo group estimated as the difference in LS means of the ANCOVA model. The least squares (LS)-mean and 95% confidence interval will be presented per treatment group together with the LS-mean placebo-corrected treatment effect and its 95% confidence interval. Statistics will be evaluated in each imputed dataset and pooled using Rubin's method (1).

10.3.2.3. Responder Analysis (CCR and Achievement of responder threshold)

All the responder analyses (CCR and achievement of responder threshold) will be analyzed using a logistic regression, with explanatory variables being the randomized treatment, and the stratification factors. Frequency and rate of responders will be reported with Clopper-Person 95% confidence intervals (CIs). For the treatment comparison, the odds ratio will be reported with 95% CI. Statistics will be evaluated in each imputed dataset and pooled using Rubin's method (1).

10.3.2.4. Correlations and scatter plots

To explore the correlation between the weight gain and the improvement on the patient reported anorexia score, the Pearson's correlation coefficient between change from baseline in Body Weight and change from baseline in 5-item Anorexia Symptom Subscale respectively will be estimated overall and within each treatment group. Analysis will be performed at each Study Visit. Same analysis will be performed using the mean change over 12 weeks.

In addition, a scatter plot of the change from baseline of the two variables will be presented (change from baseline in Body Weight at Y-axis and change from baseline in 5-IASS at X-axis), with a display of the distribution of each single variable. The analysis will be performed at each Study Visit. Same analysis will be performed using the mean change over 12 weeks.

Correlation and Scatter plot will be performed both on observed data and after imputation.

10.3.2.5. PGIS, PGIC and Hunger assessment

The PGIS and the PGIC endpoints and the hunger assessment will not be imputed, only observed value will be summarized. PGIS and PGIC are aimed to identify the responder threshold in the 5-IASS and weight. The related statistical analyses is reported separately (6, 7).

10.3.2.6. Change from baseline to Week 12 in body weight (categorical)

Additionally, absolute change from baseline in body weight to Week 12 will be categorized as follows:

- <-3 kg
- < -2 kg to >= -3 kg
- < -1 kg to >= -2 kg
- <= 0 kg to >= -1 kg
- > 0 kg to <= 1 kg
- > 1 kg to <= 2 kg
- > 2 kg to <= 3 kg
- > 3 kg.

Summary will present the number and percentage of subjects for each body weight category by treatment.

11. Safety Analysis

All safety analyses will be performed on the Safety set.

11.1. Exposure

Duration of overall exposure (days) will be calculated as the difference between last tablet intake date and the first tablet intake date plus 1.

• Duration of overall exposure (days) = date of EOT - date first tablet intake +1

Duration of overall exposure will also be calculated in weeks using the following formula:

• Duration of overall exposure (weeks) = Duration of exposure (days) / 7

Duration of overall exposure, as defined above, will include any period of temporary treatment interruption.

The duration of overall exposure in days will be summarized using descriptive statistics by treatment groups.

A contingency table by treatment groups will also be presented with the following 3-weeks categories:

- [0-3)
- [3-6)
- [6-9
- [9-12)
- [12-15)
- [15-18)
- [18-21)
- [21-24)
- ≥24 weeks.

In addition, duration of actual exposure (in days and weeks respectively) will be also calculated similarly to the duration of overall exposure but removing any treatment interruption (i.e.: considering actual differences between dates of last and first tablet intake as reported in the drug accountability for each drug kit returned).

In case a patient prematurely discontinued treatment and presented an EOT date, as recorded in the related CRF form, which is considered as implausible (i.e.: EOT date greater than 25 days after the date of the first dose of the last kit), then for calculation of actual exposure the corresponding EOT date will be replaced with the date of last visit performed + 24 days.

For patients with kit(s) not returned but with information available in the drug administration CRF form about the documented tablet intake during the applicable study visit (i.e.: the study visit during which the first tablet from the kit – then never returned – was administered), this will be used to estimate the date of last intake from the kit, adding 24 days (as maximum number of tablets available in the kit to be

regularly taken) after the first intake. This approximation will be done to derive treatment interruptions for kit(s) that were not returned. This is applicable for actual exposure calculation only.

Exposure data will be listed for all subjects in the Safety Set.

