8.8. Definitions

Baseline

The baseline value for all efficacy analyses is defined as the value collected at Visit 2 (randomization); if this is not available or collected day(s) later as compared to Visit 2, the value collected at screening visit will be used.

For the following assessments, baseline is the value reported at Screening (V1):

- ECOG PS
- HbA1c
- all Urinalysis parameters
- the Patients' Global Impression of Severity (PGIS) scale
- the Patients' Global Impression of Change (PGIC) scale

The baseline value for all safety analyses is defined as the last measurement performed before study drug administration.

Change from Baseline

Any "Change from baseline" variable will be computed as: "variable" at Visit X – Baseline, with X \geq 3 and Baseline defined as above.

Last assessment

Last assessment performed (body weight / 5-IASS) regardless of treatment discontinuation.

Retrieved dropout

Patient who drops the treatment but who continues to be assessed.

Non-monotone pattern of missingness (also called "Intermittent missing values")

Missing values may occur in the middle of a subject record (e.g., missed intermediate visit). It is expected that a value before the missing assessment, and a value after the missing assessment are available.

Monotone pattern of missingness (also called "non-Intermittent missing values")

Missing values are located in a block at the end of data records (e.g., due to study discontinuation).

Study Treatment Start Date

It is the date of the first intake of the study treatment.

End of Treatment (EOT) Date

It is the date declared in the End of Treatment CRF Form. This date will be used in the derivations unless specific adjustments are needed (e.g., for actual exposure derivation).

Last follow-up contact date

It is the date of the last contact for patients alive. It is the date of last follow-up in case of final phone contact (Visit 11 for patients completing the study, before Visit 11 in case of treatment discontinuation), or the date of last performed visit in case of patient lost to follow-up.

It corresponds to the date of death in case a patient died.

Study completion

A patient will be defined as having "completed" the study when the patient completes Visit 11. Termination of the study before performing Visit 11 will be considered as a premature study discontinuation.

Patients who completed 24 weeks treatment

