9.4. Treatment Compliance

Compliance will be evaluated overall for the Safety Set, ITT Set and Per Protocol Set.

Treatment compliance will be calculated as:

Compliance (%) = (# tablets taken / # tables to be taken according to the study schedule).

Where:

Life Sciences

tables taken = total number of tables taken between the date of first intake (included) and the date of last intake (included), as collected in the drug accountability CRF form.

tables to be taken according to the study schedule = date of Visit 10 - date of Visit 2 +1.

Date of Visit 10 will be replaced by the date of premature treatment discontinuation for patients who discontinued treatment prematurely.

In case a patient completed the treatment but missed Visit 10 or in case a patient prematurely discontinued treatment and presented an EOT date, as recorded in the related CRF form, which is considered as implausible (i.e.: EOT date greater than 25 days after the date of the first dose of the last kit), then the corresponding Visit 10 date or EOT date will be replaced with the date of last visit performed + 24 days.

If a subject returns all study medication that was dispensed, then the subject will not be classified as treated.

In case of missing drug accountability data, it will be assumed that no tablets were taken for the corresponding days with missing data.

For patients with kit(s) not returned, the information available in the drug administration CRF form about the documented tablet intake during the applicable study visit (i.e.: the study visit during which the first tablet from the kit – then never returned – was administered) will be used to add such one single day of documented treatment. For patients with kit(s) not returned and not having any information in the drug administration CRF form, i.e., there is no evidence that at least one tablet was taken, the number of tables taken will be assumed as 0.

A patient will be considered compliant with the therapy if his/her overall compliance is higher or equal to 80%.

Compliance will be reported numerically using descriptive statistics and categorically (using categories <80%, $\ge80\%$ to $\le100\%$, and >100%), by treatment group.

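### SAP 11.1 defines overall exposure by last tablet intake but computes it from the End of Treatment form date, and late form dates that the SAP calls implausible are not corrected there

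*SAP*

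**What the plan says.** SAP 11.1 gives the end of overall exposure twice. The sentence reads "Duration of overall exposure (days) will be calculated as the difference between last tablet intake date and the first tablet intake date plus 1". The formula that follows reads "Duration of overall exposure (days) = date of EOT - date first tablet intake +1". SAP 8.8 defines the EOT date this way: "It is the date declared in the End of Treatment CRF Form". Nothing there equates it with the last tablet. The same entry says the date is used as recorded unless a specific adjustment is needed, and names actual exposure as its example.

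Section 11.1 also sets a plausibility test for patients who discontinued prematurely. The trigger is "EOT date greater than 25 days after the date of the first dose of the last kit", and the remedy is "then for calculation of actual exposure the corresponding EOT date will be replaced with the date of last visit performed + 24 days". Section 9.4 applies the same test to compliance: "then the corresponding Visit 10 date or EOT date will be replaced with the date of last visit performed + 24 days".

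The descriptive statistics by arm and the table in 3-week categories are specified for overall exposure, which includes temporary interruptions by design. Actual exposure is derived as well, with interruptions removed.

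**The concern.** One variable has two end dates, and the SAP does not say which governs. Two programmers working from 11.1 could produce different tables. The two dates cannot be assumed equal, because the SAP itself expects some EOT dates to be too late for the last kit and corrects them in two other derivations. If the formula is followed, dates that the SAP rejects elsewhere enter the exposure summary.

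The separation could be long. Patients who stop study drug are asked to keep attending visits up to Week 24, so contact with the site can continue well after the last tablet. What is at stake is an accurate description of how long patients took the drug, which is the background against which the safety tables are read.

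**Working it through.** The documents state no exposure figure, so there is none to reproduce. The check is date arithmetic.

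**Inputs from the documents**
- Kit size: at most 24 tablets (SAP 11.1), one a day.
- Trigger for an implausible date: EOT more than 25 days after the first dose of the last kit, so 26 days or more (SAP 11.1).
- Replacement date: last visit performed plus 24 days (SAP 11.1 and 9.4).
- Completers take the last dose at Visit 10, Day 169 to 172 (protocol 6.1.10).

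**Completers.** With the first tablet on Day 1 and EOT at Visit 10, either definition gives 169 to 172 days. That is 169/7 = 24.1 to 172/7 = 24.6 weeks, in the top category. The definitions differ only when the EOT date is not the last tablet date.

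**Smallest excess in a flagged patient, no interruption.** If the last kit starts on day L, its last possible tablet is on day L + 23. A flagged EOT date is day L + 26 or later, so the excess is at least 26 − 23 = 3 days. Against the replacement date, when the last visit is the kit-start visit, the excess is at least 26 − 24 = 2 days. The trigger catches late dates only.

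**Illustration.** Assumptions: first tablet on Day 1; last kit started on Day 43, which was also the last visit; no interruption. The EOT lags are assumed, because the documents give none. The last possible tablet is on Day 43 + 23 = Day 66, so first-to-last-tablet time is at most 66 days (9.4 weeks, category [9-12)). The replacement date would give 43 + 24 = 67 days, in the same category.

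| EOT after kit start | Overall exposure by formula | Category | Excess over 66 | Excess over 67 |
|---|---|---|---|---|
| 26 days | 69 days (9.9 weeks) | [9-12) | 3 | 2 |
| 40 days | 83 days (11.9 weeks) | [9-12) | 17 | 16 |
| 60 days | 103 days (14.7 weeks) | [12-15) | 37 | 36 |
| 90 days | 133 days (19.0 weeks) | [18-21) | 67 | 66 |

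**Effect on an arm mean.** Shift = proportion affected × mean excess in days. Both are assumed. At 1% and 2 days it is 0.01 × 2 = 0.02 days; at 10% and 60 days it is 0.10 × 60 = 6 days.

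**Would copying the existing replacement rule work?** Not always. Take a retrieved dropout whose last kit started on Day 64, with EOT on Day 90 (flagged, since 90 − 64 = 26) and last visit on Day 169. The replacement date is Day 169 + 24 = Day 193. That is 103 days later than the date it corrects, although the kit's last possible uninterrupted tablet was on Day 64 + 23 = Day 87.

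**The case against.** The strongest reply is that overall exposure is meant as a crude span from first dose to declared end of treatment, with actual exposure as the refined measure. SAP 8.8 lends this some support by naming actual exposure as the place for adjustments. If the declared EOT date is the date of the last dose, sentence and formula agree and nothing is lost. That part stands: the documents contain no form-completion instruction showing that the two dates usually differ. It does not remove the contradiction, because the sentence in 11.1 says last tablet and the SAP does not trust every EOT date.

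A reader might infer more than the documents support:

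- *That the exposure table does overstate time on drug, or does so more in one arm.* No count, lag or split by arm is given.
- *That flagged dates are impossible.* The SAP calls them implausible. A patient who pauses dosing can spread 24 tablets over more than 25 days, and overall exposure includes pauses. In the 60-day row of the illustration, a pause of 103 − 66 = 37 days would make the last tablet fall on the EOT date, and the excess would vanish.
- *That the correction is confined to actual exposure throughout the SAP.* Section 9.4 makes it for compliance too, which makes its absence from overall exposure harder to explain.
- *That adverse event rates are distorted.* SAP 11.2.3 plans patient counts, percentages and event counts; none uses exposure as a denominator.

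There is also a fair objection to a simple fix. For an unreturned kit the only documented intake may be the visit dose that opened it. Ending exposure there would discard up to 23 further days of possible dosing.

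**Conclusion.** The derivation is wrong as written: the formula does not implement the definition, and overall exposure keeps EOT dates that the SAP replaces for actual exposure and compliance. The summary and 3-week table can therefore overstate first-to-last-tablet time in patients who discontinued prematurely with a late EOT date. For a flagged patient without interruption the excess is at least 3 days, and long lags can shift one or more categories (one at the assumed 60 days, three at 90).

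The overall extent is unknown. The arm-mean range of 0.02 to 6 days rests entirely on assumed proportions (1% to 10%) and assumed excesses (2 to 60 days), and the shift is nil wherever EOT equals the last tablet date. This is a descriptive safety summary. The co-primary and secondary efficacy tests and the adverse event percentages do not depend on it.

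**What to change.** In SAP 11.1, make the formula match the sentence:

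1. End overall exposure at the last tablet intake date from drug accountability, minus the first intake date, plus 1. Interruptions stay included.
2. Where the last kit was not returned or the last intake date is missing, use the recorded EOT date if it passes the SAP's own plausibility test.
3. Otherwise use the first dose of the last kit plus the SAP's 24-day kit allowance, never later than the recorded EOT date or death.
4. Do not carry the rule of last visit plus 24 days into overall exposure, because it can lengthen exposure in retrieved dropouts.

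The cost is a wording change and somewhat more derivation work, mainly for the fallback. Intake dates for returned kits are already collected in drug accountability. Reported exposure may become slightly shorter.
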